#### Other data collection tools:

Aside from demographics (age, gender, housing situation, social support, marital status, service connection, employment, education), we will also collect data about depression symptoms and patient's perception of care coordination for subgroup analysis and risk adjustment.

**Depression symptoms – The Patient Health Questionnaire-8 (PHQ-8, appendix)** is a 8-item well validated self-administered instrument that is a reliable measure of depression severity and depression symptom burden and is responsive to treatment outcomes over time. Scores can range from 0 to 24, with a higher score indicating a greater burden of depressive symptoms. PHQ-8 scores of 5, 10, and 20 represented mild, moderate, and severe depression, respectively. Internal reliability estimates range from 0.86 to 0.89 using Cronbach's alpha. Two day test-retest reliability is estimated to be 0.84 with nearly identical mean total scores. The advantages of the PHQ-8 include the following: 1) It is self-administered; 2) It contains only 8 questions that help identify patients with clinically meaningful symptoms of depression; 3) Can be reasonably administered in 5-10 minutes; and 4) Can be scored in 1-2 minutes. For safety guards in place regarding suicidal ideation, please refer to Human Subjects section.

**Perceived patient-centeredness and coordinated care (PACIC survey) (Appendix):** The PACIC is a well-validated 20-item questionnaire that has 5 subscales: Patient Activation, Delivery System Design/Decision Support, Goal Setting, Problem-solving/Contextual Counseling, Care Coordination; with the various scales, as well as the overall score, to be both internally consistent and moderately stable during test-retest. This tool assesses the health care system from the patient's perspective (patient centeredness). The questions are general enough that we can ask the patient to answer in the context of their heart disease care.

**Medical co-morbidities and cardiac history:** based on the Charlson Co-morbidity index, this data will be collected through chart abstraction by our research assistants at baseline and confirm it with patient and caregiver. The Charlson Co-morbidity index is a weighted index that takes into account the number and the seriousness of comorbid disease. The index is well validated for its ability to predict risk of death from co-morbidities at 1-year and 10-year follow-up periods. We will also obtain cardiac testing data including echocardiography, cardiac catheterization, and stress test data through review of medical records. Non-VA sources will be contacted if indicated to track non-VA care (Table 1 of data collection below)

Table 1. Timeline of Data Collection	Baseline	90 days	180 days	Data Source
Charlson Comorbidity Index	X			Patient, family and chart
Caregivers / Demographics	X			Patient, family and chart
Echocardiography, cardiac testings	X			Patient and chart
KCCQ, EQ-5D	X	X	X	Patient
HF Self-care Index, PACIC, PHQ-8, BNP	X	X	X	Patient
Patient (± caregiver) satisfaction	Ongoing			Interview
Provider perception	Ongoing			Interview
Hospital admission or death	Ongoing			Patient, family and chart
HF clinics / programs	Ongoing			Patient, family and chart
Outpatient physician and ER visits	Ongoing			Patient, family and chart

#### 9. Quantitative Analytic Plan:

Aim 1: To compare between the intervention versus usual care arms in the change from baseline in KCCQ (Primary outcome) and EQ5D (secondary outcome) at 90 and 180 days. The analysis will be performed from an intention to treat principle. First, descriptive statistics (mean, standard deviation, median, inter-quartile range, and frequency distribution) will be calculated to summarize, at baseline, patients' demographic and comorbidities including previous hospitalizations, cardiac history (heart function and coronary disease), medical and health service utilization information (including medication possession ratio, HF self-care index, BNP levels, enrollment into HF clinics / programs, visits with primary care and cardiologists), and the primary outcome of interest (KCCQ, overall score) according to randomized arms. Log-transformation of variables and outcomes of interest will be performed to approximate normality when appropriate. Linear mixed-effects (LME) model will be utilized for the analysis of this aim, where the response variable is KCCQ, fixed effects include treatment group, time (0 = baseline, 1 = at 90 days, 2 = 180 days), treatment group by time interaction, and other important demographic variables identified in the descriptive analysis, and random effects include site-specific random intercept, subject-specific random intercept (nested within site) and subject-specific random slope of time. This modeling approach has been shown to provide an unbiased and efficient estimate of the longitudinal treatment effect in a variety of situations, such as in the presence of missing data, imbalance of the primary outcome at baseline, and covariance heterogeneity between treatment groups. In this way, we could compare the intervention effects at 90 days and whether residual effects exist at 180 days. The random site effect is used to model the clustering effect of patients in the same study site and random subject effects are used to model the variability in the subject-specific trajectory and the correlation of repeated measures within subject. Residual analysis will be conducted to examine the appropriateness of the functional forms of each fixed effect, and Information criteria (AIC, BIC) will be used to choose the correlation structure.

Secondary: Same modeling technique will be used to study EQ5D as the outcome instead of KCCQ.

Aim 2: To compare between the intervention versus usual care arms in hospitalization or death at 90 and 180 days after the randomization. For this analysis Cox proportional hazards model will be utilized where the event is a composite outcome that represents either hospitalization or death. Any patient who does not experience the event by 180 days will be denoted as censored. The main exposure is treatment group and other covariates include patient demographic and comorbidity information as described above. We will examine the differences in outcome at both 90 and 180 days. The appropriateness of the proportional hazards assumption will be examined and any violation of the assumption will be addressed. The appropriateness of the functional forms of each covariate will be assessed through residual analysis.

Aim 3: To compare between the intervention versus usual care arms in the change from baseline in patient's (a) HF Self Care index and (b) BNP levels, we will use the same linear mixed-effects modeling approach as described in Aim 1.

Subgroup and Sensitivity Analyses: In order to understand potential heterogeneity of treatment effects, stratified analyses will be conducted by our randomization stratifiers such as co-interventions or not, ejection fraction ( $\geq 40\%$  &  $< 40\%$ ), and hospitalizations in the previous 6 months ( $> 2$  &  $\leq 2$ ). Given that baseline KCCQ scores, HF self-care behavior, comorbidity burden, depression symptoms and caregiver support could potentially change the outcome of HF, we will conduct test for multiplicative interaction between the condition of interest (e.g. depression with PHQ-8  $\geq 10$  vs.  $< 10$ ) and the study arm allocation (intervention vs. usual care arm) on the patient outcomes of interest described in Aims 1 and 2. *If any these interaction terms are significant at an alpha level of 0.05 or less*, subgroup analyses will be conducted (e.g. number of comorbidities below and above the median, baseline KCCQ scores above and below the median, and by presence or absence of significant depression symptoms or caregiver support) depending on the feasibility by sample size. Sensitivity analyses will be performed by study site to determine the impact of setting in our study findings and potential variation of findings.

Mediating Factor Analyses: In order to understand the mechanisms by which HF-SMA improves health status and hospitalization or death, we will explore potential mechanisms from the process measures such as HF-self-care index and perceived care coordination (PACIC survey). In order to prove mediation, four conditions must be met: (1) correlation between the change in treatment variable (HF-SMA or not) with the change in mediator (change in process measure, e.g. HF self-care index); (2) variation in the mediator must be correlated with variation in the outcomes (e.g. KCCQ); (3) controlling for the mediator substantially reduces or eliminates the relationship between the treatment and outcomes; and (4) the treatment variable must temporally precede the mediator, which is inherent in our study because enrolled patients will be treatment naive. We will

compare multivariate regression model specifications that serially exclude and include the potential mediators and the treatment variable.

Exploratory Analysis on Study Generalizability and External Validity: We will compare the baseline characteristics and study outcomes of enrolled patients with those in the Registry of Excluded patients to assess for potential differences in characteristics and outcomes. If there are significant differences in baseline characteristics, an “as treated” analysis will be performed to compare on the study outcomes while adjusting for differences in baseline characteristics between excluded patients and patients who received HF-SMA using the same approaches we described for Aims 1 and 2. Although we understand that the excluded patients may be fundamentally distinct from the study population, these analyses will help to make inferences on the potential effects of the intervention on untreated patients and explore the generalizability of our findings.

Missing Data Issues: Since these are primary data collected as part of a clinical trial, we do not anticipate significant missing data. We will also record and report all reasons for dropout and missing data, and account for all patients in our reports as well as study publications. Overall, if the number of observations with missing values is small (<5%), we will conduct analyses by removing the variables with missing values. If the number of observations with missing values is many, we will compare characteristics between dropouts and those who had completed all the study visits. If it is determined that missing data is random, we will resort to methods that impute values, SAS Proc MI and MIANALYZE readily impute maximum likelihood estimates from incomplete data. If significant differences are found in the attrition rates across study arms, both ‘intention to treat’ and ‘as treated’ analyses will be performed to determine the extent to which the missing data may be biasing the results. For the ‘intention to treat’ analysis, we will generate actual random raw data values suitable for filling in gaps in an existing database. Typically, five to ten databases are created in this fashion. We will then analyze these data matrices using an appropriate statistical method, treating these databases as if they were based on complete case data. The results for these analyses are then combined into a single summary finding.

Sample Size and Power Considerations: The overall study sample will be 375 (225 patients from Phoenix VAMC and 150 patients from Providence VAMC). Statistical power for the aims 1 and 2 is estimated given these are the most relevant and the most restrictive in terms of power estimations. Under a conservative dropout rate of 15% for 180 days of follow-up for the main outcomes (Aims 1 and 2), we estimate the power with an effective sample size of 316 (15% less than the total sample) and a 2-sided significance level of 0.05 using nQUERY Advisor 7.0®. For aim 1, we assess the power to detect a clinically significant change in KCCQ of 5 points, assuming a baseline score of 63 (our preliminary studies), with a common standard deviation of 15 for the study arms, using a 2-sample t-test. For aim 2, we assess the power to detect a relevant decrease in rehospitalization or death risk of 25-30% at 180 days using a Cox Proportional Hazards model. Based on our preliminary data of 20,000 Veterans with ejection fraction <40% hospitalized with HF, their rehospitalization rates at 6 months is ~40%. Assuming similar event rates for rehospitalization or death, as shown in Table 2, we have good power to detect the proposed outcomes at very conservative estimates of effective sample size (n=158 in each arm, which is 85% of the total proposed recruitment target). Repeated measures at 90 and 180 days are also likely to add to the statistical power in Aim 1 to detect differences at the subgroup levels.

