### **Primary Aim:**

Aim 1: To determine whether HF patients who participate in HF-SMA, as compared to usual care, experience better cardiac health status measured by Kansas City Cardiomyopathy Questionnaire (primary outcome), and overall health status (EQ-5D, secondary outcome), from baseline to 90 and 180 days.

*Hypothesis: HF patients who participate in HF-SMA will experience better cardiac and overall health status than patients who receive usual care from baseline to 90 and 180 days after randomization.*

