8. Study Visits, Data Collection and Study Outcomes: There will be 3 research visits: 1) baseline for enrollment consent and data collection, and 2) at 90 days (+ or - 30 days) and 3) at 180 days (+ or - 30 days) after randomization for outcome collection, in addition to monthly phone calls in between study visits. All surveys will be self-administered unless the patient prefers otherwise. Only experienced interviewers will conduct the interviews, proficiency must be demonstrated to site PI. Training for the qualitative aspects of the study will be provided by the Cleveland site. All patient self-reported measures and interviews will be performed during the three research study visits. To accommodate patients, per request, study visits may be conducted over the phone or in a private location of their choosing with two study members present. Also to further accommodate patients, per request, de-identified surveys using only a study ID number may be mailed out along with a postage paid, self addressed return envelope. Patients will be instructed not to include their name on any of the returned surveys. Research assistants must demonstrate proficiency in data collection techniques to the site PI's.

Aim 1: Primary outcome is change in KCCQ and secondary is change in EQ5D.

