**Table 2. Power / Effect Size Calculations at 180 days Intervention vs. Usual Care**

Aim 1: Difference in KCCQ		Aim 2. Risk of Rehospitalization or death	
Difference in mean KCCQ	Power	Hazard Ratio	Power
4.5	.76	0.74	0.75
5	.84	0.73	0.80
5.5	.90	0.71	0.85
6	.95	0.69	0.90

10. Qualitative Analysis: All interviews will be audio recorded and fully transcribed. We will use qualitative data analysis software, NVivo (QSR International, Melbourne, Australia) to organize, code and retrieve qualitative data, summarize linkages across themes and maintain analytic notes of the coders. Transcripts and field notes from observations of the intervention (not video recorded for privacy reasons) to monitor fidelity will be entered in the database and line- by-line open and thematic coding will be conducted to identify key themes/factors. Qualitative data analysis will be conducted through an iterative process in which members of the research team engage in both data collection and analyses throughout the study. This allows for researchers to refine

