**11. Limitations and potential shortfalls:** First, it is possible that secular trends such as an increase in the availability for co-interventions threaten our experimental design and cause underestimation of our treatment effects. We are using stratified randomization to balance current co-interventions and will track this carefully during the enrollment period. Adjusted analyses for imbalanced in exposure to co-interventions during follow-up will be performed when necessary and stratified analyses by co-interventions will also be explored as detailed in our analysis plan. In addition, it is likely that the effects of secular trends should be randomly distributed in a randomized controlled study, such that co-interventions should not have a differential effect. Second, our study duration is only 6 months. Based on our previous data on diabetes, the effect of SMAs on patient's outcomes are the highest while the patient is enrolled in the program and gradually declines after the stop of sessions unless booster sessions are planned. Given limitation of resources, we would like to test the short and mid-term effectiveness of the intervention first, prior to studying maintenance programs. Third, there is always a risk of not achieving the targets for patient recruitment. Fortunately, the project team is very experienced, and has had excellent track records in patient recruitment and retention in previous studies of similar characteristics. The use of 2 study sites will provide us with additional protection to achieve recruitment goals. Fourth, variation in effect size: It is possible that we found that the intervention may be effective in one site but not another, or in certain patient subgroups but the overall effect may not be large. This problem can arise due to distinct standards of usual care provided to patients and different settings of care. However, understanding these differences through this study will be important to know which settings and patients to target to derive the most benefits.

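### The primary KCCQ comparison is set at 90 and 180 days with no decisive contrast, order or either/both rule, so the two-sided 0.05 is not guaranteed and Table 2's 0.84 covers only one test at one visit

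*Combined protocol and SAP*

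**What the plan says.** - **Specific Aims, Primary Aim.** The hypothesis is that HF-SMA patients "will experience better cardiac and overall health status than patients who receive usual care from baseline to 90 and 180 days after randomization". Both visits are named, without a rule for combining them.
- **Section 8, outcome line.** It reads "Aim 1: Primary outcome is change in KCCQ and secondary is change in EQ5D" and gives no time point. The 90- and 180-day visits, each with a window of 30 days either way, appear in the visit schedule of the same section.
- **Section 9, Aim 1.** The comparison is "change from baseline in KCCQ (Primary outcome) and EQ5D (secondary outcome) at 90 and 180 days". The analysis is one linear mixed-effects model with treatment, time coded 0, 1, 2, their interaction, and a subject-specific random slope of time. The plan does not say which coefficient or contrast decides the aim, or whether the fixed effect of time is categorical or linear. It says that with this model "we could compare the intervention effects at 90 days and whether residual effects exist at 180 days".
- **Section 9, Sample Size and Power Considerations.** One level is given, "a 2-sided significance level of 0.05", with no split or order. The Aim 1 power is for a two-sample t-test.
- **Table 2.** Its title is "Power / Effect Size Calculations at 180 days Intervention vs. Usual Care". No day-90 power is given.
- **Section 11, second limitation.** Citing the team's diabetes data, the plan says that SMA effects "are the highest while the patient is enrolled in the program and gradually declines after the stop of sessions", unless boosters are planned. Section 1 (Overview) describes four sessions over 8 weeks, or as clinic appointments allow, and no boosters.

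**The concern.** The primary outcome yields at least two treatment comparisons, and the plan does not say which result, or which combination, meets Aim 1. Three things follow.

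1. The type I error of the primary claim depends on a rule that has not been written down. Some possible rules keep 5% and others do not.
2. The stated power belongs to a single test. It does not describe a primary outcome assessed at two visits.
3. Benefit at day 90 without benefit at day 180 is a plausible pattern given how Sections 9 and 11 describe the time course. The plan offers a descriptive reading of it (an effect without a residual) but does not say whether it meets the primary aim. In an open-label trial with a patient-reported primary outcome, that choice should not be left until the data are in.

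**Working it through.** **Inputs from the documents.** 158 analysable patients per arm; SD 15; difference 5 points (Table 2 also shows 4.5, 5.5 and 6); two-sided alpha 0.05; sessions over 8 weeks; visits at days 90 and 180.

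**Inputs not in the documents, assumed.** The correlation r between the day-90 and day-180 test statistics (range 0 to 0.9), and any size of effect at day 180 below 5 points.

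**Step 1. Reproduce Table 2, Aim 1.** Standard error = 15 × √(2/158) = 1.688. For 5 points the expected Z is 5/1.688 = 2.963, so power ≈ Φ(2.963 − 1.960) = Φ(1.003) = 0.842.

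| Difference | Normal approximation | Exact t | Table 2 |
|---|---|---|---|
| 4.5 | 0.760 | 0.758 | 0.76 |
| 5 | 0.842 | 0.840 | 0.84 |
| 5.5 | 0.903 | 0.901 | 0.90 |
| 6 | 0.945 | 0.944 | 0.95 |

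The table is right for one test at one visit at two-sided 0.05.

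**Step 2. Rule A: significance at either visit meets the aim.** Error rate = 1 − P(|Z1| < 1.96 and |Z2| < 1.96), with Z1 and Z2 bivariate normal with correlation r. For r = 0 this is 1 − 0.95² = 0.0975.

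| r | 0 | 0.5 | 0.8 | 0.9 |
|---|---|---|---|---|
| Error rate | 9.75% | 9.1% | 7.8% | 7.0% |

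A Bonferroni split (0.025 per visit) would restore 5%, but power for 5 points at a given visit falls from 0.84 to 0.76. Recovering 0.84 takes 189 per arm, or 2 × 189 / 0.85 = 445 randomised with 15% dropout, against 375 planned.

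**Step 3. Rule B: both visits must be significant.** The error rate stays at or below 5%. Power = P(Z1 > 1.96 and Z2 > 1.96) with both means at 2.963, that is, 5 points at each visit. This gives 0.746 at r = 0.5 and 0.781 at r = 0.8, so about 0.75 to 0.78.

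**Step 4. Rule C: one interaction coefficient.** If time 0, 1, 2 is fitted as linear, there is a single treatment-by-time slope b and one test at 0.05. The modelled difference in change from baseline is then 1 × b at day 90 and 2 × b at day 180. That model forces the effect to double between the visits, so it cannot show an effect at 90 days that has faded by 180.

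**Step 5. Day 180 as the powered visit.** If sessions start at randomization, 8 weeks is 56 days. Day 90 is then nominally 90 − 56 = 34 days after the sessions, and day 180 is 180 − 56 = 124 days after. With Table 2's inputs, single-test power is 0.66 if the day-180 difference is 4 points (4/1.688 = 2.370; Φ(0.410) = 0.659) and 0.43 if it is 3 points (3/1.688 = 1.778; Φ(−0.182) = 0.428). These differences are illustrations; the documents give no amount of waning.

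**The case against.** A reader might infer that the plan breaks its 0.05 level. The documents do not support that. The inflation in Step 2 needs a rule that either visit suffices, and no such rule is stated. The hypothesis joins the visits with a conjunction, which can be read as requiring both, and then 5% holds. A linear-time interaction would also be a single test. This objection stands: the level is not guaranteed, which is weaker than saying it is exceeded. It does not remove the gap, because the plan chooses none of these rules and they differ in error rate, power and meaning.

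A reader might also infer that the plan expects the heart failure effect to have waned by day 180 and has therefore powered the wrong visit. That too goes further than the text. The decline in Section 11 comes from diabetes data and carries no figure. Section 9 treats a residual at 180 days as a question, and the hypothesis claims benefit there. Sessions nominally end before day 90 as well, may run later with clinic availability, and both visits have wide windows, so day 180 is less favourable only in relative terms. Powering day 180 is not an error in itself. The dropout allowance is also set for 180 days, and one can read the section as intending day 180 as the main time point.

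What remains is a mismatch of emphasis. The analysis text puts the effect at day 90 and the residual at day 180, while the power table covers day 180 alone.

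The sample size section says repeated measures are likely to add power for Aim 1, but with reference to subgroup differences and without a figure, so this does not settle which test 0.84 refers to.

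**Conclusion.** The concern holds as a gap in the decision rule. Section 9 and the Primary Aim place the primary KCCQ comparison at two visits without a decisive contrast, order or either/both rule, so the stated two-sided 0.05 is not guaranteed. Depending on the rule adopted:

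- either visit suffices: error 7.0% to 9.75% (assumed r from 0.9 to 0);
- both visits required: error at or below 5%, power about 0.75 to 0.78 for 5 points at each (assumed r from 0.5 to 0.8);
- one named visit: error 5%, power 0.84 for 5 points, which is the only case Table 2 describes.

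The documents do not establish that 0.05 is breached, that the effect will have faded by day 180, or that day 90 must come first. The power values for a reduced day-180 effect are sensitivity figures resting on an assumed amount of waning. This is a cheap improvement that should be made before the analysis.

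**What to change.** 1. In the Primary Aim, the Section 8 outcome line and Section 9 (Aim 1), state that the fixed effect of time is categorical and name the treatment contrast in KCCQ change from baseline at one visit as the primary test, at two-sided 0.05.
2. Test the other visit at two-sided 0.05 only if the first is significant. This fixed sequence keeps the overall error rate at 5% without splitting alpha.
3. The order is the sponsor's choice. Day 90 then day 180 fits Section 9's wording; day 180 then day 90 fits Table 2. Both are equally valid for error control.
4. Label the Aim 1 column of Table 2 with the chosen primary visit. If day 90 is chosen, 0.84 carries over on the same n, SD and 5-point difference; the 15% dropout was set for 180 days, and 5 points at day 90 is itself an assumption. If day 180 is chosen, add power for a smaller effect as a sensitivity, for example 0.66 at 4 points and 0.43 at 3 points, marked as assumed waning.

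**Cost.** Wording only: no added patients or visits, and no alpha penalty on the first test. The downside is that the second visit cannot be claimed if the first fails. The chance of winning both when the difference is 5 points at each visit is the 0.75 to 0.78 of Step 3.

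### The Aim 1 model codes visit as 0/1/2 without saying it is categorical; fitted as a number, it would report a sustained 5-point KCCQ benefit as about 2.5 to 2.6 at day 90

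*Combined protocol and SAP*

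**What the plan says.** Section 9, Aim 1, sets out a linear mixed model for KCCQ: "fixed effects include treatment group, time (0 = baseline, 1 = at 90 days, 2 = 180 days), treatment group by time interaction". The random effects are a site intercept, a subject intercept and a "subject-specific random slope of time". The stated purpose is: "In this way, we could compare the intervention effects at 90 days and whether residual effects exist at 180 days". A model check is planned: "Residual analysis will be conducted to examine the appropriateness of the functional forms of each fixed effect". No alternative form for time is given in case that check fails.

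The model is reused. For EQ-5D, "Same modeling technique will be used to study EQ5D as the outcome instead of KCCQ"; for HF self-care and BNP in Aim 3, "we will use the same linear mixed-effects modeling approach as described in Aim 1". Section 8 (Study Visits, Data Collection and Study Outcomes) places the follow-up visits "at 90 days (+ or - 30 days) and 3) at 180 days (+ or - 30 days) after randomization". Aim 1 names both follow-up visits and ranks neither. The power calculation in Table 2 is for 180 days only.

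**The concern.** The wording allows two models. The numeric codes, the random slope and the mention of functional forms point to time as a number. The sentence on 90-day and residual 180-day effects points to a separate effect at each visit.

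The two models answer different questions. With numeric time, one interaction coefficient carries the whole treatment effect on change, as a straight line from zero at baseline. Such a model can show neither a benefit that levels off nor one that fades, so it cannot make the comparison the paragraph promises. No fade has to be assumed for this to matter: a benefit reached by day 90 and simply held is already misreported.

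Two analysts following the text could therefore publish different day-90 results from the same data. For a sustained benefit, one would report about half of the 5 points that section 8 gives as the minimal clinically important change. The same applies to EQ-5D, HF self-care and BNP.

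**Working it through.** **1. The plan's own figure.** Inputs from section 9, Sample Size and Power Considerations: 158 per arm after 15% dropout, SD 15, two-sided 0.05, two-sample t-test. SE = 15 × √(2/158) = 1.688. Power by the noncentral t for differences of 4.5, 5, 5.5 and 6 is 0.758, 0.840, 0.901 and 0.943. Table 2 prints 0.76, 0.84, 0.90 and 0.95, so it reproduces to within 0.01. This calculation uses day 180 alone and does not involve the time coding.

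**2. The constraint.** With numeric t = 0, 1, 2, the fitted arm difference is g + b·t. The arm effect on change from baseline is (g + b) − g = b at day 90 and (g + 2b) − g = 2b at day 180. The 1:2 ratio holds whatever the data show.

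**3. What b estimates.** I used generalised least squares with 187 per arm, a random intercept and slope, and variances treated as known. The documents give no variance components or dropout timing, so these are assumptions. The base SDs are intercept 11, slope 3 and residual 9, for a total SD of 14.2 to 15.4, near the plan's 15. The expected b is a weighted sum of the true arm differences at the three visits:

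| Dropout | Baseline | Day 90 | Day 180 |
|---|---|---|---|
| None | −0.500 | 0.000 | 0.500 |
| 7.5% before day 90, 15% by day 180 | −0.514 | 0.029 | 0.486 |
| All 15% after day 90 | −0.523 | 0.046 | 0.477 |

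Day 90 carries almost no weight in its own estimate.

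**4. Fitted change effects (day 90, day 180).** The true profiles are illustrative.

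| True | Complete data | 7.5%/15% dropout |
|---|---|---|
| (5, 5) | (2.5, 5.0) | (2.57, 5.14) |
| (5, 3) | (1.5, 3.0) | (1.60, 3.20) |
| (5, 0) | (0, 0) | (0.14, 0.29) |

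Example, second column: 5 × 0.029 + 3 × 0.486 = 1.60. Two other SD sets, (13, 2, 7) and (9, 4, 11), and the later dropout pattern give 2.57 to 2.62 at day 90 for (5, 5). Across all these cases with dropout, the day-180 error is 0.13 to 0.46 points.

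These figures are for change from baseline, which is the Aim 1 quantity. The fitted raw arm difference at day 90 for (5, 5) is about 3.3, because the group term absorbs roughly 0.76 as a spurious baseline difference (0.76 + 2.57 = 3.33).

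**5. Interval coverage at day 90.** Coverage = Φ(1.96 − d) − Φ(−1.96 − d), with d = (5 − b)/SE. For (5, 5) in the base set, 7.5%/15% dropout: d = (5 − 2.572)/0.773 = 3.14, giving 12%. Over the three SD sets the range is 1% to 28%. Section 8 reports an observed KCCQ spread of 27.8 (n = 32). Scaling all SDs by 27.8/15 gives 60%, range 39% to 72%. The bias does not change with the scale; the miss rate does.

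**6. Categorical visit.** The mean model is saturated, so (5, 5) is recovered as (5, 5). Standard errors, base set, 7.5%/15% dropout: day 180 is 1.547 numeric and 1.548 categorical; day 90 is 0.773 numeric and 1.396 categorical, or (1.396/0.773)² = 3.3 times the variance.

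**The case against.** The strongest reply is that the plan's purpose settles the reading. Aim 1 asks for effects at two named visits, numeric time cannot deliver them separately, the codes may be mere visit labels, and a random slope can sit alongside a categorical fixed effect. This stands as evidence of intent. It does not remove the ambiguity, because nothing in the model statement says categorical and other phrases in the paragraph suggest a numeric term.

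A second reply is that the residual check would expose the misfit. It may: with three visits and two arms, observed and fitted means are easily compared. But no fallback model is named, so the replacement would be chosen after seeing the data.

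A third is that the sized comparison is untouched. That is right for practical purposes, and it limits the point to day 90.

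A reader might infer more than the documents support, in three ways:

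- *That the plan specifies a wrong model.* It does not; it leaves the model open.
- *That the plan itself expects the effect to fade by day 180, so a day-90 benefit would be wiped out.* Section 11 describes fading from diabetes SMA data. The 30-day visit windows and sessions timed by clinic availability leave the course in HF open. The fading profiles are illustrations only.
- *That the day-90 interval would almost always miss the truth.* That depends on the SD, as step 5 shows.

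**Conclusion.** The point holds as an ambiguity in the primary-outcome model with a definite consequence under one of its two readings. If time is fitted as coded, a sustained 5-point KCCQ benefit is reported at day 90 as 2.5 (complete data) to about 2.6 (15% dropout), and an effect that fades is understated further. The 1:2 ratio is algebraic; the figures with dropout rest on assumed variance components and dropout timing, and move little across those tried. The day-180 estimate is exact with complete data and off by about 0.1 to 0.5 points with dropout.

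Coverage of the day-90 interval for a sustained effect is about 1% to 28% at a total SD near 15, and 39% to 72% at the scale of the observed 27.8. The 27.8 is a single-site spread printed beside a median, so both ranges should be read as assumptions. The text should be settled before analysis; the trial's design and sample size are not called into question by this point.

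**What to change.** State in section 9 that visit is a three-level categorical fixed effect (baseline, 90 days, 180 days), with arm-by-visit contrasts on change from baseline at days 90 and 180. Keep the stated subject random effects or use an unstructured covariance. Apply this to KCCQ, EQ-5D, HF self-care and BNP. Name day 180 as the primary contrast, which matches Table 2.

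The cost is wording only, since Table 1 already schedules all four measures at all three visits. Day 180 loses no meaningful precision. The day-90 standard error rises from 0.77 to 1.40 at an SD near 15; the smaller value is valid only if the effect really grows in a straight line from baseline.

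A separate improvement, also free: adjust for the randomisation strata in section 5 (site, co-intervention, prior hospitalizations, ejection fraction below 40%) in place of "other important demographic variables identified in the descriptive analysis". The strata are fixed in advance, whereas those covariates would be picked after looking at the data.
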